6.2 Data handling

Missing data can have an impact upon the interpretation of the trial data. In general, values for missing data will not be imputed unless otherwise specified. For baseline value, if it is missing at baseline visit, then the latest non-missing value of screening will be used to replace.

All serum HBV DNA results below the lower limit of detection (<20 IU/mL) or results of “not detected” will be analyzed as being the value of the lower limit of quantification, which is 20 IU/mL. For patients whose week 240 visits were influenced by COVID-19, a safety follow-up were added for these subjects. The missing week 240 will be imputed from safety follow-up visit in the analysis of primary endpoints. Please refer to section 7.4 for details.

7. STATISTICAL ANALYSIS

7.1 Subject screening, disposition and protocol deviations

The screening failure subjects and the reasons for screening failure will be summarized by the numbers and percentages. The percentages are based on the number of screening failure subjects.

The disposition of subjects will be summarized, including the numbers and percentages of subjects for the following categories: all enrolled subjects, subjects completed the study, subjects early discontinued from the study, subjects in the modified intent to treat population, subjects in the per-protocol population, and subjects in the safety analysis population. All percentages are based on the number of all enrolled subjects.

The primary reason for subject premature discontinuation from study will also be summarized. The reasons for discontinuation will include voluntarily discontinue participation, lost to follow-up, lack of efficacy, subjects with treatment interruptions of ≥ 28 consecutive days, adverse event, intercurrent illness, protocol violations, pregnancy, and other reason. A listing will be provided.

Major protocol deviations will be summarized and listed for mITT population. Subject counts and percentages will be displayed by the following deviation categories:

- Eligibility criteria not met
- Excluded medication, vaccine or device
- Assessment or time point completion
- Wrong study treatment/administration/dose

Major protocol deviations which results in the exclusion of the subject from PP population will be discussed, determined, and documented by study team before final database lock. A listing of subject disposition in analysis data sets will be provide.

7.2 Subject Information

7.2.1 Demographics and baseline characteristics

Demographic include subject age, sex (Male/Female), race (Asian/Others), and baseline characteristics for subjects include subject height, weight, BMI, systolic blood pressure, diastolic blood pressure, pulse, respiratory rate, body temperature, liver stiffness measurement, LSM for patient with $ALT > ULN$ or $ALT \leq ULN$, creatinine level, serum phosphorus, eGFR, creatinine clearance rate, HBV DNA, alcohol abuse, drug abuse, history of medication hypersensitivity, family history of hepatitis B and hepatoma, liver cirrhosis, hypertension, HBeAg, Childs-Pugh score, ALT, liver biopsy, and HBV genotype. Age will be calculated as the difference of the year of informed consent date and year of birth. Percentages for categorical data will be calculated based on the number of subjects in the analysis set of the corresponding population. Descriptive statistics will be used for continuous data. Listings of demographics and baseline characteristics will also be provided.

Age (Year) = Year of Informed Consent Date - Year of Birth

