## **3. INVESTIGATIONAL PLAN**

### **3.1. Study Design**

This is a prospective, multi-centre, open-label, cohort study to investigate efficacy and safety of Tenofovir Disoproxil Fumarate (TDF) treatment in Chinese CHB subjects with advanced fibrosis and compensated cirrhosis. The study will enrol 186 subjects with a diagnosis of CHB and advanced fibrosis or compensated cirrhosis.

Screen phase ( $\leq 4$  weeks): Written informed consent must be obtained from each subject prior to participation in the study. Subjects considered eligible to enroll in the study will be assessed at a screening visit as described in Table 1 to decide if they meet the study criteria (see that in 4.2 and 4.3). Between Screen visit and baseline visit, subjects will not receive investigational product.

Treatment phase: 186 subjects will be administered TDF 300 mg QD and undergo regular safety and efficacy assessments every 12 weeks for a total of up to 240 weeks (see Table 1). Subjects will be questioned about adverse events, concurrent medications, and study drug accountability; blood will be taken for hematology and biochemistry profiles; serum samples will be tested for HBV markers, and the prothrombin time will be measured. Serum samples will be collected at Week 12, 24,36, 48, 60, 72, 84, and 96 and every 24 weeks thereafter and analyzed for HBV DNA levels at a central laboratory. Abdominal ultrasound, the prothrombin time and serum alpha-fetoprotein test will be performed every visits. If abdominal ultrasound reports a liver mass or nodule, CT or MRI will be performed. At baseline and W216, 100 of subjects will take liver biopsy to

evaluate liver histological changes pre and post TDF treatment. All subjects will be followed through to Week 240.

Rescue treatment could be optionally initiated in subjects with unsatisfied response to TDF, at the discretion of the investigator if

- subjects have confirmed virological breakthrough as defined by  $\geq$  one log increase in HBV DNA from nadir determined by two sequential HBV DNA measurements at least 1 month apart, or
- subjects have HBV DNA  $\geq$ 200IU/ml at week 48 and afterwards have  $\leq$  one log decrease in HBV DNA at two consecutive visits, confirmed by a third visit at least one month apart.

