### 4.2. Inclusion Criteria

Specific information regarding warnings, precautions, contraindications, adverse events, and other pertinent information on the GSK investigational product or other study treatment that may impact subject eligibility is provided in the IB/IB supplement(s) and product label.

Deviations from inclusion criteria are not allowed because they can potentially jeopardise the scientific integrity of the study, regulatory acceptability or subject safety. Therefore, adherence to the criteria as specified in the protocol is essential.

Subjects eligible for enrolment in the study must meet all of the following criteria:

1. Age 18-60 years(inclusive);
2. Presence of HBsAg in serum at screening and for at least 6 months before screening assessment;
3. Serum HBV DNA  $\geq$  2000 IU/mL if HBeAg positive at screening (with or without ALT elevation); or serum HBV DNA  $\geq$  200IU/mL if HBeAg negative at screening (with or without ALT elevation);
4. Pathologically or clinically diagnosed as advanced fibrosis or compensated cirrhosis defined as one of following(a or b) :
  - a. Liver biopsy showing advanced fibrosis or cirrhosis (Ishak score  $\geq$ 4 or Fibrosis stage  $\geq$ S3 by Scheuer Score, or within the previous 6 months before baseline and provided that no treatment likely to improve liver histology has been taken since). The slides must be available for review by an independent histopathologist.
  - b. Clinical diagnosis: liver stiffness measure (LSM)  $>$ 12.4 kpa (ALT  $>$  ULN) or LSM  $>$ 9.0 kpa (ALT  $\leq$ ULN), (See section 6.2.7) plus one of the following:
    - i. Endoscopy-proven gastroesophageal or gastric varices, non-cirrhotic portal hypertension excluded;
    - ii. Abdominal ultrasound or CT found changes indicating cirrhosis, irregular liver surface or nodularity, with/without splenomegaly(depth of spleen  $>$ 4.0cm or spleen length  $>$ 13cm);
    - iii. Blood platelets  $<$ 100  $\times 10^9/L$  (and other causes of thrombocytopenia excluded);

5. Ability to give written informed consent;
6. A female is eligible to enter and participate in this study if she is of:
  - a. non-childbearing potential (i.e., physiologically incapable of becoming pregnant, including any female who is post-menopausal), or

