- 3 In the event of early study drug discontinuation, the evaluation should be performed in 12 weeks after discontinuation of study treatment.
- 4 Medical history will include any acute and chronic medical conditions including prior surgery, information related to hepatitis B history, any current and prior HBV medications, and previous HBV-related procedures.
- 5 Update any new medical conditions and/or concomitant medications that have occurred since study screening.
- 6 Concomitant medications including traditional Chinese medicines and/or herbal remedies.
- 7 At screening, a complete physical examination will be performed. For all following indicated visits, a brief physical examination will be performed.
- 8 Including blood pressure, pulse, respiratory rate and temperature.
- 9 Urine pregnancy test will be performed at screening, baseline and every 3 months after dosing.
- 10 HBV DNA will be tested using Roche COBAS Taqman HBV test(LLD 20 IU/mL).
- 11 Each study visit: All study medication to be collected and reconciled.

- 12 Liver biopsy will be done in 100 subjects in sites at baseline and week 216. Liver biopsy can be done at screening (Visit 1) or at baseline (Visit 2), at the discretion of investigator. Liver biopsy slides within 6 months prior to baseline can be accepted as baseline evaluation.
- 13 Tests will be performed at central lab
- 14 Demographic data includes birth date, gender and race
- 15 B ultrasound examination include liver, pancreas, spleen, gall bladder and kidney
- 16 Urinalysis: urine glucose, ketones, specific gravity, blood, pH and protein
- 17 Serum will be collected as scheduled for potential resistance surveillance. Genotypic analysis will be performed under the condition defined in protocol (see section 6.2.8)
- 18 Genotyping will be performed at central lab at screen

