7.2.3 Inclusion and exclusion criteria

Subjects must meet all specified inclusion and none of the exclusion criteria in order to be eligible to participate in the study. Inclusion and exclusion criteria information will be presented in the listing.

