The relationship between baseline variables or on-treatment variables and improvement of fibrosis will be analysis by univariate and multivariate logistic model. Univariate analysis will include gender, age, BMI category (< 25 or ≥ 25 kg/m²), baseline HBV DNA (≥ 2000 or < 2000 , IU/mL), baseline HBeAg sero-status, baseline ALT value, baseline LSM value, baseline total bilirubin, HBeAg loss at Week 24, treatment response at Week 24 and Week 48, ALT normalized or not at Week 24 and Week 48, change from baseline of LSM at Week 12 and Week 24, change from baseline of GGT at Week 24. Multivariate analysis will include sex, age and the factors with $P \leq 0.20$ in univariate analysis.

Proportion of LSM improvement will be summarized at Week48, Week96, Week144, Week192 and Week240 for patients with baseline LSM result in following groups: LSM improved (LSM decreased from baseline $\geq 30\%$), LSM stable (LSM decreased from baseline $< 30\%$ or no change from baseline), and LSM deteriorate (LSM increase from baseline).

Proportion of fibrosis stage improvement will be summarized at Week 48, Week 96, Week 144, Week 192 and Week 240 for patients of fibrosis stage measured by fibrosis improved from baseline, ≥ 2 stage fibrosis stage improved from baseline, ≥ 1 stage fibrosis stage, no change from baseline, fibrosis stage increase from baseline.

Analyses of correlation coefficients between LSM and ALT level will be analyzed by Pearson correlation coefficients and P-value during every 48 weeks by patients with ALT normal at baseline, patients with abnormal at baseline and overall.

Correlation coefficients between variables change at Week 12 and 24 and LSM change at Week 240 will be analyzed by correlation coefficients and P-value. The change from baseline of Gamma-Glutamyltransferase (GGT), Total Bilirubin (TBIL), Albumin (ALB), International Normalized Ratio (INR) and LSM will be included in the analysis of correlation coefficients at Week 12, platelets (PLT), GPR, APRI, FIB-4 and all the variables included at Week 12 will be included in the analysis of correlation coefficients at Week 24.

A 5-years predicted HCC risks by REACH-B model (see Section 8.5) and observed HCC risks (cumulative incidence of HCC) at Week 240 will be presented in table. Decline in LSM from baseline to Week 240 by visit will be analyzed by a line plot.

In addition, a listing of HBV DNA result will be provided for the following patients:

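### SAP 7.2.1 takes age as consent year minus birth year, so reported age can exceed completed age by one year and show an eligible 60-year-old as 61

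*SAP*

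**What the plan says.** SAP 7.2.1 (Demographics and baseline characteristics) gives the rule in words, "Age will be calculated as the difference of the year of informed consent date and year of birth", and again as a formula, "Age (Year) = Year of Informed Consent Date - Year of Birth". The SAP contains no other definition of age.

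Protocol 4.2, criterion 1, sets the entry range: "Age 18-60 years(inclusive". SAP Appendix 1 repeats it. A footnote to Table 1 of the protocol states "Demographic data includes birth date, gender and race", so the exact date of birth is available.

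Eligibility is handled elsewhere. Protocol 3.1 places the check against the entry criteria of 4.2 and 4.3 at screening: "Subjects considered eligible to enroll in the study will be assessed at a screening visit as described in Table 1 to decide if they meet". On the same subject, SAP 7.2.3 says only that "Inclusion and exclusion criteria information will be presented in the listing".

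Age is also an input to Cockcroft-Gault clearance, eGFR and FIB-4 (SAP 8.4), to REACH-B (SAP 8.5), and to the multivariate models in SAP 7.4.3, which always include sex and age. None of these sections says which age is meant.

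**The concern.** A difference of calendar years equals completed age only if the birthday has already passed on the consent date. Otherwise it is one year too high, and it is never too low. Entry limits such as 18 and 60 are ordinarily read in completed years, so the reported age and the entry criterion are on different scales.

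Two things are at stake:

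- **Consistency of the report.** The demographics table and listing could show ages above 60 while the eligibility listing (Listing 2.4) shows criterion 1 as met. Someone would have to explain an apparent breach that never happened. At the lower limit, the reported age would hide a real breach.
- **Clarity of the derived quantities.** With one age definition and several formulas that need an age, a programmer may carry the 7.2.1 value into all of them or may choose another. The results differ, and the SAP does not settle the choice.

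**Working it through.** The documents give no figure for the share of subjects affected, so there is none to reproduce.

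**Inputs.** From the documents: the age rule (SAP 7.2.1), limits 18 and 60 (protocol 4.2), 186 subjects (protocol 4.1), the REACH-B age coefficient 0.09859 and P0 = 0.99650 (SAP 8.5). Assumed: birthdays even over the year. Consent dates are taken as even for the central case and varied for the range, because the documents give no enrolment calendar.

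**1. Share overstated.** Let u be the consent date and v the birthday, as fractions of the year. Year difference minus completed age is 1 if v > u and 0 otherwise, so P(overstated) = 1 − E[u].

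| Consent dates | E[u] | Overstated by 1 year | Of 186 |
|---|---|---|---|
| First quarter only | 0.125 | 87.5% | about 163 |
| First half only | 0.25 | 75% | about 140 |
| Even over the year | 0.50 | 50% | 93 |
| Second half only | 0.75 | 25% | about 47 |
| Last quarter only | 0.875 | 12.5% | about 23 |

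**2. Entry limits.** A subject aged 60 with a birthday still to come that year is shown as 61. A 17-year-old in the same position is shown as 18.

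**3. REACH-B, if the 7.2.1 age is used.** Risk = 1 − 0.99650^exp(F), with 0.09859 per year of age in F. One extra year multiplies exp(F) by exp(0.09859) = 1.104. The examples are men with ALT ≥ 45:

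| Profile | Completed age | Risk | Risk one year up | Ratio |
|---|---|---|---|---|
| HBeAg negative, HBV DNA 10^5 to 10^6 − 1 | 45 | 3.54% | 3.90% | 1.10 |
| HBeAg positive, HBV DNA ≥ 10^6 | 45 | 6.58% | 7.23% | 1.10 |
| HBeAg positive, HBV DNA ≥ 10^6 | 55 | 16.67% | 18.23% | 1.09 |

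For the first row, F = 0.78798 + 0.96311 + 2.27028 + 0.09859 × 45 − 6.12796 = 2.33.

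If half the subjects are affected, the mean hazard factor against completed years is (1 + 1.104)/2 = 1.052.

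**4. The same rule against exact decimal age.** The error is then v − u. With even consent dates its mean is 0.00 year, and the mean hazard factor is 1.001. With all consents in the first or last quarter the mean error is +0.375 or −0.375 year.

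**5. Creatinine clearance (Cockcroft-Gault), if the 7.2.1 age is used.** At baseline, 61 in place of 60 gives (140 − 61)/(140 − 60) = 79/80, or −1.25%. If that age is kept fixed at consent, the sign reverses later. An affected 45-year-old is recorded as 46 but is about 49.6 at Week 240 (240 weeks is about 4.6 years), and (140 − 46)/(140 − 49.6) = 94/90.4, or +4.0%.

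**The case against.** The strongest reply is that this is a demographics derivation with little reach. Much of that stands, and three tempting readings have to be set aside.

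- **A reader might infer that the formula admits 17-year-olds.** The documents do not support this. Criteria are assessed at the screening visit, and the SAP only lists the eligibility data. Age eligibility can also still be verified, because the birth date is on file. What remains is that the reported age would not reveal such a subject.
- **A reader might infer that REACH-B predictions are inflated and TDF therefore looks more protective.** This needs the 7.2.1 age to be the model input and the model to require completed years, and the SAP states neither. Against decimal age there is no average inflation under even consent dates. The prediction is also exploratory: "A 5-years predicted HCC risks by REACH-B model (see Section 8.5) and observed HCC risks" are simply set out in a table, and the protocol plans no comparisons. Even a 5% relative shift moves a 6.58% prediction by about 0.33 percentage points, against a planned margin of error of 3.4 points on the observed HCC incidence.
- **A reader might infer that clearance is biased downwards.** If age is fixed at consent, that holds only near baseline. Later in the study the error runs the other way.

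The reply does not dispose of the rule itself. It is stated twice, it is the only definition of age, and it can contradict criterion 1 in the reported tables.

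**Conclusion.** The point holds and is minor. For every subject whose birthday falls after consent in the calendar year, the SAP overstates completed age by exactly one year. The 50% share rests on even birthdays and even consent dates; the range of 12.5% to 87.5% covers enrolment confined to a single end quarter.

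The certain consequence is in reporting. Table 2.1.1 and Listing 2.1.1 can show an eligible subject outside the entry range and cannot expose one who was a year too young.

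The consequence for REACH-B is conditional: 9-10% relative in an affected subject's predicted risk in the examples worked here, measured against completed years, and only if this age is the one used. The HCC primary endpoint, whether as a nominal proportion or by Kaplan-Meier, does not involve age. Disease progression involves it only through the creatinine-clearance component, where the size and sign of the effect depend on which age is used, and the SAP does not say.

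**What to change.** - In SAP 7.2.1, define age as completed years at informed consent from the full dates: year difference, minus 1 if the month and day of consent precede the month and day of birth. In SAS, INTCK('YEAR', birth, consent, 'C') does this. Use it for the demographics outputs and for any check of age against the entry range.
- Avoid the shortcut floor((consent − birth + 1)/365.25). For birth on 1 January 2000 and consent on 31 December 2017 it gives 6575/365.25 = 18.001, hence 18, when completed age is 17.
- In SAP 7.4.3, 8.4 and 8.5, state which age (completed or exact decimal, at consent or at the visit) enters the models, creatinine clearance, eGFR, FIB-4 and REACH-B.
- Keep the year difference only where day or month of birth is missing, and flag those subjects.

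The cost is a few lines of SAP text and one derivation in code. No new data are needed.

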7.2.2 Medical history

Medical history will include any acute and chronic medical conditions including medication of

chronic hepatitis B, medical history/current medical conditions, history of treatment, relevant surgeries. Medical history will be listed by system organ class and preferred term coded in MedDRA 17.0.

7.2.3 Inclusion and exclusion criteria

Subjects must meet all specified inclusion and none of the exclusion criteria in order to be eligible to participate in the study. Inclusion and exclusion criteria information will be presented in the listing.

7.3 Treatments and medications

7.3.1 Prior and concomitant medication

Prior medication is defined as all the drugs taken by the subjects prior to the first dose date of TDF.

Concomitant medication is defined as all the drugs taken by the subjects from the first dose date of TDF to completion of the study.

If medication start date is on or after the date of first dose of study drug, then medication will be summarized as concomitant medication regardless of whether medication end date is missing or not.

If medication end date is before the date of first dose of study drug, then medication will be summarized as prior medication regardless of whether medication start date is missing or not. Note that medication that started prior to the date of first dose of study drug and continued after dosing will be summarized as prior medication and separately as concomitant medication.

All medications will be coded according to WHO drug dictionary (Version: WHODDE 2016Q3) and Anatomical Therapeutic Chemical (ATC) coding.

Prior and concomitant medications will be listed separately. Medication class, medication name, indications, total daily dose, unit, route, start date and end date will be presented in the listing.

7.3.2 Exposure of TDF and treatment compliance

Exposure of TDF information including dose start date, end date, duration of study drug and dosing compliance will be presented in the listing.

The duration in days of study drug exposure from first dose date to the last dose date will be summarized by descriptive statistics, including n, mean, sd, Q1, median, Q3, range.

The duration of the drug exposure (day) = Last dose date - First dose date + 1

Treatment compliance, defined as actual taken amount divided by expected taken amount per protocol times 100, will be summarized by descriptive statistics for mITT. The formulas for calculating the treatment compliance are as follows:

Treatment Compliance (%) = Actual taken amount × 100 / Expected taken amount

Drug accountability information including date (dispensed or returned), dispensed amount, returned amount, lost amount, expected taken amount, actual taken amount, missing amount, and treatment compliance will be presented in the listing.

7.3.3 Rescue Treatment

Rescue treatment information including rescue treatment name, frequency, reason taken, other reason taken, start date, end date will be presented in the listing. If no patient received rescue treatment, the listing will not be presented.

7.3.4 Non-drug therapies

Non-drug therapy information including therapy details, start and end date, and the reason for use will be presented in the listing. If no patient received rescue treatment, the listing will not be presented.

